Currently, Medicare patients who are readmitted within 30-days could result in significant fines to healthcare providers and institutions. Innovations in healthcare delivery aided by device technology that expeditiously facilitates positive airway pressure therapy could mitigate such financial liabilities. Averaged Volume Assured Pressure Support –Auto EPAP (AVAPS-AE) device can not only prevent the nocturnal hypoventilation due to COPD, but also treat coexisted obstructive sleep apnea ⁽⁶⁾. AVAPS-AE is a mode of therapy (Philips Respironics Inc, Monroeville, Pa) with potential advantages over the currently established modes of noninvasive positive pressure ventilation (CPAP and bi-level therapy). This mode of therapy incorporates AVAPS (automated adjustable IPAP setting to maintain target ventilation with a settable rate of change), Auto EPAP and Auto Back up Rate. It automatically adjusts EPAP in response to patient events such as snores, leaks, and apneas / hypopneas, provides an automatic back up rate and automatically adjusts pressure support in order to maintain the target tidal volume. In a prospective cohort study, Marin and colleagues have shown that positive airway pressure (PAP) therapy treatment for “COPD-OSA overlap syndrome” can reduce a composite index of hospitalizations and mortality ⁽⁷⁾. A prospective multi-center study of PAP therapy aimed at reducing re-hospitalization due to COPD has not been performed.

A Pilot, Multi-Center, Randomized, Open-Label, Parallel Group Study to Assess the Effects of a Novel Application of Averaged Volume Assured Pressure Support Ventilation (AVAPS-AE) therapy on Re-hospitalization in Patients with Sleep-Disordered Breathing with co-morbid COPD.

Confidential

II. Study Design

This is a multicenter, randomized, parallel-group, open label study of the efficacy of AVAPS-AE to prevent re-hospitalization in hospitalized patients with comorbid COPD. A wash-in period – aimed at assessing device tolerance – will be performed in order to exclude participants who are at high risk for discontinuing positive airway pressure (PAP) therapy. Similar to pharmaceutical studies, such a wash-in period for medication tolerance can help reduce attrition and missingness that can adversely affect study sample size estimations.

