Over the first 30 days post discharge, participants in the intervention arm will receive 3 phone calls to promote PAP therapy and medication adherence. Participants in the standard of care (SOC) arm will also receive 3 phone calls to promote medication adherence over the first 30 days post discharge. On days 30 and 60, all participants will receive a phone call to determine if they had been admitted to the hospital, or had an unplanned visit to a physician’s office or emergency room. Information regarding hospital

A Pilot, Multi-Center, Randomized, Open-Label, Parallel Group Study to Assess the Effects of a Novel Application of Averaged Volume Assured Pressure Support Ventilation (AVAPS-AE) therapy on Re-hospitalization in Patients with Sleep-Disordered Breathing with co-morbid COPD.

Confidential

admission, diagnostic tests, medication changes, and procedures will be collected from all participants. Discharge summaries of re-hospitalizations and office or ER visits, as well as diagnostics tests and therapies received will be collected for measuring healthcare costs.

Participants who enrolled in a registry (optional) for a 3 year follow-up will also be queried on a yearly basis regarding hospitalizations, cardiovascular events, and assessment of vital statistics in the National Death Index registry. The study will conclude when all randomized participants have been followed for a minimum of 60 days. An independent Data Safety and Monitoring Committee (DSMC) will monitor safety data on an ongoing basis and may recommend that the study be stopped earlier in case of safety concerns. No Interim efficacy analyses is planned. Ongoing DSMB review is planned to assess device and/or safety related clinical events and adjudicate if applicable. This will be performed after 25%, 50% and 75% of target enrollment have been completed. Participants will be followed for occurrence of death or hospitalization throughout the duration of the study for a minimum of 24 months after randomization. All death and hospitalization reports will be collected on an ongoing basis during the study and will be adjudicated by an adjudication committee consisting of three site investigators.

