4. Number of hospitalizations over 3 years (optional if enrolled in registry)
5. Time to re-hospitalization alone
6. Composite end-point of time to occurrence of non-emergent healthcare utilization (such as scheduled hospitalization, scheduled physician office, urgent care visits or emergency room visits).

IV. Subject Selection

Inclusion criteria:

1. Hospitalized patients who are at high risk for readmission who are at least 18 years of age.
2. Specifically patients with (a) a primary or secondary admission diagnosis of COPD who are ready for discharge AND (b) are also found to have sleep-disordered breathing (AHI \geq 10 per hour; $>3\%$ oxygen desaturation for hypopneas) by overnight portable respiratory study prior to hospital discharge.
3. Bedside spirometry revealing evidence for obstructive lung disease (post-bronchodilator; GOLD stage II or greater (FEV1 $<70\%$ predicted post BD).
4. No previous home PAP or NIV use within the past year

Exclusion criteria:

1. Central sleep apnea (Central apnea index >5 per hour; and/or $>50\%$ are central apneas & hypopneas)
2. Clinically unstable, i.e., hypotensive shock, uncontrolled cardiac ischemia or arrhythmias, requiring life support ventilation or as otherwise determined by the investigator
3. Participants with Stage III & IV Chronic Heart Failure as defined by the New York Heart Association (NYHA) Classification
4. Known or expected contraindications for the use of non-invasive ventilation per the assessment of the investigator.

A Pilot, Multi-Center, Randomized, Open-Label, Parallel Group Study to Assess the Effects of a Novel Application of Averaged Volume Assured Pressure Support Ventilation (AVAPS-AE) therapy on Re-hospitalization in Patients with Sleep-Disordered Breathing with co-morbid COPD.

Confidential

5. Lack of medical insurance

V. Study Enrollment

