A Pilot, Multi-Center, Randomized, Open-Label, Parallel Group Study to Assess the Effects of a Novel Application of Averaged Volume Assured Pressure Support Ventilation (AVAPS-AE) therapy on Re-hospitalization in Patients with Sleep-Disordered Breathing with co-morbid COPD.

Confidential

intervention and SOC groups will receive \$150.00 as compensation for participating in the study. Compensation will be pro-rated based on completion of study milestones.

Information regarding admission, diagnostic tests, medication changes, and procedures will be collected from all participants. Discharge summaries of re-hospitalizations and office or ER visits and diagnostics tests and therapies received will be collected for measuring healthcare costs.

Participants will be asked if they would be interested enrolling in a registry for a 3 year follow-up. This will involve participants being contacted on a yearly basis inquiring about any hospitalizations, cardiovascular events, and assessment of vital statistics in the National Death Index registry. Participants who elect to enroll the registry will receive an additional \$25 in compensation.

Transition Plan:

Upon completion of the study or earlier termination, site investigators will cooperate with the study participants' primary health care providers regarding continuity of care to assure that participants receive appropriate follow-up care after the conclusion of the study. Study participants who are randomized to the treatment group, where a therapeutic benefit is evident, will be allowed to keep the provided AVAPS device until a similar replacement device can be provided to the participant through usual care pathways as part of this transition plan. Study participants who are randomized to the SOC group will have the option of receiving an AVAPS unit at the end of the 60 day period if prescribed and provided through the usual care pathway of their healthcare provider as part of this transition plan. The risk of additional and on-going device supplies not being covered by insurance or involving co-pays will be explained to the participant within the consent. Philips will not be responsible for providing device maintenance or study supplies after the 60 day study period.

Study Process Flow:

Study Procedures	Hospital Procedures (Pre-Discharge)	Post Discharge Study Procedures	Post 60 Day Study Procedures
Informed consent	X		
Inclusion/Exclusion Review	X		
Medical History Assessment	X		
Vitals	X		

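### The 3-year hospitalization endpoint is measured only in people who choose at Day 60 to join a registry, so randomisation does not protect an arm comparison on it

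*Combined protocol and SAP*

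**What the plan says.** All references are to the combined protocol and SAP.

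- Section III, secondary endpoint 4: "Number of hospitalizations over 3 years (optional if enrolled in registry"). It stands among the other secondary endpoints with no exploratory or descriptive label.
- Section VI, Day 60: "Participants will be asked if they would be interested enrolling in a registry for a 3 year follow-up". In the Study Process Flow the registry row is marked only under "Post 60 Day Study Procedures".
- Section II: "Participants who enrolled in a registry (optional) for a 3 year follow-up will also be queried on a yearly basis regarding hospitalizations". Registry follow-up also covers cardiovascular events and vital status from the National Death Index.
- Section II on blinding: "This is a multicenter, randomized, parallel-group, open label study".
- Section VI, Transition Plan: SOC participants "will have the option of receiving an AVAPS unit at the end of the 60 day period if prescribed" and supplied through usual care. Intervention participants with evident benefit may keep the study device until usual care replaces it.
- Section II on follow-up: one sentence ends the study once every randomised participant has at least 60 days of follow-up. A later sentence has participants followed for death or hospitalization "for a minimum of 24 months after randomization".
- Section VII (Statistical Analysis): the analysis times are 30 and 60 days. No 3-year analysis, start date or treatment of non-joiners is given.

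**The concern.** Randomisation makes the arms comparable at the time of allocation. Endpoint 4 is defined on a subset formed about 60 days later by survival, continued contact and willingness to join. All three can depend on how a participant fared on an arm that he or she knew. Someone doing well on the device, or someone in the SOC arm disappointed not to have had it, may be more or less inclined to sign up. If the people who join differ in prognosis between arms, the 3-year counts will differ even if AVAPS-AE does nothing.

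The second problem is what the count would measure. Almost all of the three years follows a point at which either arm's device use may change for reasons that include prescription and perceived benefit. A difference, or the lack of one, could not be credited to the 60-day intervention. Because the item is listed as a secondary endpoint of a randomised trial, a reader of the results could take it for a randomised comparison.

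**Working it through.** **Inputs from the documents.** Up to 80 enrolled, a goal of 60 completers and 25% attrition (Section V); transition at Day 60 (Section VI); a 3-year count (Section III). The plan gives no 3-year hospitalization rate, registry uptake or rate of later device use. These are assumed below and varied.

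**The plan's own figure.** 60 / (1 − 0.25) = 80, which matches Section V.

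**Numbers available.** If 40% to 80% of 60 completers join (assumed), the registry holds 60 × 0.40 = 24 to 60 × 0.80 = 48 people, both arms together.

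**Share of the window after Day 60.** 60 / (3 × 365.25) = 5.5%, so 94.5% of the three years comes after the transition.

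**Selection with no true effect.** Assume that in each arm half the participants have 0.5 and half 1.5 hospitalizations per year. If a share L of the low-risk half and H of the high-risk half join, the mean rate among joiners is

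(0.5 L + 1.5 H) / (L + H).

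| Uptake L/H, AVAPS-AE | Uptake L/H, SOC | Mean rates | Rate ratio |
|---|---|---|---|
| 60%/60% | 60%/60% | 1.000 / 1.000 | 1.00 |
| 70%/50% | 70%/50% | 0.917 / 0.917 | 1.00 |
| 70%/50% | 60%/60% | 0.917 / 1.000 | 0.92 |
| 80%/40% | 60%/60% | 0.833 / 1.000 | 0.83 |
| 80%/40% | 40%/80% | 0.833 / 1.167 | 0.71 |
| 50%/70% | 60%/60% | 1.083 / 1.000 | 1.08 |
| 40%/80% | 60%/60% | 1.167 / 1.000 | 1.17 |

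Example, fourth row: (0.5 × 0.8 + 1.5 × 0.4) / (0.8 + 0.4) = 1.0 / 1.2 = 0.833. Overall uptake is 60% in both arms in every row, so equal overall uptake would not rule the distortion out.

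**Later device use in the SOC arm.** Assume a true rate ratio of 0.70 that is constant over time, with the intervention arm staying on the device. If a fraction c of SOC participants starts AVAPS at Day 60, the ratio after Day 60 is 0.70 / ((1 − c) + 0.70 c):

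- c = 25%: 0.70 / 0.925 = 0.76
- c = 50%: 0.70 / 0.850 = 0.82
- c = 75%: 0.70 / 0.775 = 0.90

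**Follow-up statements.** A study that ends after a minimum of 60 days per participant does not deliver a minimum of 24 months for everyone. Apart from the optional registry and the transition plan, the Study Process Flow marks only quality-of-life questionnaires in its last column. No listed procedure would supply hospitalization data to 24 months in people outside the registry.

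**The case against.** The strongest reply is that bias has not been shown. Entry after randomisation distorts the comparison only if survival or uptake relates to prognosis differently in the two arms, and nothing in the documents says that it will. This stands. A reader might infer that the endpoint is biased, or biased in favour of AVAPS-AE; the table shows that the distortion may be nil or run either way.

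Second, the plan states no 3-year test. Section VII stops at 60 days, no specific aim mentions three years, and the endpoint is marked optional. This also stands: there is no stated 3-year claim to refute. But an endpoint listed without a method, start date or status leaves the comparison open to be made later.

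Third, a reader might treat SOC access to the device as a further bias. The documents do not support that. Access depends on prescription and usual care, and some sites may already start PAP earlier under their usual pathway (Section VI, SOC Group). Under a treatment-policy estimand, later uptake is part of the comparison and dilutes it. It is a problem only if the count is read as the effect of 60 days of therapy, or of continued therapy against none; the plan names no estimand. Nor do the documents fix whether joining comes before or after an SOC participant obtains a device.

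Fourth, a reader might think that the 24-month statement contradicts an optional registry. It need not. Registry members are queried in addition, so the registry could sit on top of follow-up of everyone. The conflict is with the 60-day sentence in the same section.

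Last, this is a pilot, and the primary endpoint is untouched. That is true and limits the weight of the point, but the correction is cheap.

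**Conclusion.** The point holds as one about protection, not about demonstrated bias. Endpoint 4 is restricted to people selected after randomisation, with the arm known, so a between-arm comparison on it lacks the protection of randomisation. Under the assumed two-risk-group model with no true effect, the ratio lies between 0.71 and 1.17, and is 1.00 if uptake depends on risk in the same way in both arms. That range rests on invented uptake and event rates. It shows what is possible and does not predict the result.

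Separately, with about 94.5% of the window after Day 60, the count cannot isolate the effect of 60 days of AVAPS-AE. This follows from the documents alone. The 60-day and 24-month follow-up statements in Section II contradict each other and must be reconciled. The primary endpoint and the 30- and 60-day analyses are not affected.

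**What to change.** 1. Ask for registry consent with the main written consent (Section V), before randomisation, so that entry cannot depend on arm or early outcome.
2. Define the 3-year period as starting at randomisation. Include everyone who consented, with death as a terminal event. The recurrent-event methods already named in Section VII allow for this, and the registry already plans a National Death Index check.
3. Report registry uptake, deaths and retention by arm. Show baseline severity of those followed as well, since overall uptake can be equal while its make-up differs.
4. Label the comparison beyond Day 60 as descriptive, and state how later device use in either arm is to be read.
5. Reconcile the two follow-up statements in Section II. If all randomised participants are in fact followed for 24 months, use those data for the longer-term hospitalization comparison: they cover 24 of the 36 months without registry selection. The descriptive label still applies, because most of that period also follows Day 60.

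The cost is one consent item moved earlier, a few sentences in Sections II, III and VII, and IRB review of the revised consent. Uptake at baseline may differ from uptake at Day 60, dropout over three years can still differ by arm, and the 3-year result will carry less inferential weight. Sample size and the primary analysis do not change.

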AVAPS-AE is a mode of therapy (Philips Resironics Inc, Monroeville, Pa) with potential advantages over the currently established modes of non-invasive positive pressure ventilation (CPAP and bilevel therapy). This mode of therapy incorporates AVAPS (automated adjustable IPAP setting to maintain target ventilation with a settable rate of change), Auto EPAP and Auto Back up Rate. We believe that these automated parameters will allow better nocturnal ventilatory control to offset the differing elastic and resistive loads imposed by changes in body position during sleep. Furthermore, AVAPS-AE will counter the changing ventilatory requirements due to alterations in lung volumes and airway resistance during different stages of sleep. In summary, the AVAPS-AE mode will enable automatic adjustment in response to ventilatory changes throughout the night. The device platform used in this study with the AVAPS-AE feature is in the BiPAP A40 platform. This device uses existing modes of therapy, therapy features, and algorithms as that which have been previously cleared by the Food and Drug Administration (FDA) (K121623).

III. Study Objectives/Endpoints

Specific aim #1: Evaluate the effects of novel application of Averaged Volume Assured Pressure Support (AVAPS-AE) therapy on time to (# of days) emergent and non-emergent healthcare utilization in patients with sleep-disordered breathing who are hospitalized with co-morbid COPD.

Specific aim #2: Evaluate the effects of novel application of Averaged Volume Assured Pressure Support (AVAPS-AE) therapy on the number of emergent and non-emergent healthcare utilization over 6 months;

A Pilot, Multi-Center, Randomized, Open-Label, Parallel Group Study to Assess the Effects of a Novel Application of Averaged Volume Assured Pressure Support Ventilation (AVAPS-AE) therapy on Re-hospitalization in Patients with Sleep-Disordered Breathing with co-morbid COPD.

Confidential

costs related to re-hospitalization; number of visits to physician offices or emergency rooms, and health-related quality of life (disease-specific and general HR-QOL measures).

Primary Endpoints

Composite end-point of time to occurrence of emergent healthcare utilization (such as re-hospitalization, unscheduled physician office visits, urgent care visits or emergency room visits).

Secondary Endpoints:

1. Healthcare Costs
2. Change in quality of life (SF-36) at 30 and 60-days
3. Change in quality of life (FOSQ) at 30 and 60-days

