- One week Device Adherence Assessment (Intervention Group)

During the first 2-7 business days post discharge, research staff will evaluate participant's device adherence via remote download. Participants with poor adherence to AVAPS-AE at home (adequate adherence defined as \geq 4 hours of use on at least 5 of the first 7 nights) will not be included in the "per-protocol analysis" (Such participants will, however, be considered in the intention to treat analysis). Per the investigators discretion, the device setting parameters may be adjusted at this time.

- Weekly Phone Follow-ups (Initial 30 days only):

Phone calls will be made weekly (\pm 2 business days) by the study coordinator to assess mask interface issues (Intervention group) and encourage adherence to AVAPS-AE (Intervention group) and medications (both intervention and SOC group). If participants require an additional visit related to issues noted above, this visit may occur either in the home or as an office to the study site.

- Day 30

At 30 days (\pm 2 business days) post discharge, participants in both Intervention and SOC groups will receive a phone call to determine if they had been admitted to this hospital, or had an unplanned visit to a physician's office or emergency room. Participants will be asked to complete FOSQ and SF-36 questionnaires. Participants will be given the option of completing the questionnaires verbally via phone call or completing handwritten copies and returned via direct mail. Postage paid return envelopes will be provided to participants who elect to complete and return the surveys by mail.

- Day 60

On day 60 (\pm 2 business days), participants in both Intervention and SOC groups will receive a phone call to determine if they had been admitted to this hospital, or had an unplanned visit to a physician's office or emergency room. Participants will be asked to complete a final FOSQ and SF-36 questionnaire. Participants will be given the option of completing the questionnaires verbally via phone call or completing handwritten copies and returned via direct mail. Postage paid return envelopes will be provided to participants who elect to complete and return the surveys by mail. Participants in both

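### Urgent care and emergency room visits are listed in both the emergent primary composite and the non-emergent secondary endpoint 6, with no rule assigning an event to one of them

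*Combined protocol and SAP*

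**What the plan says.** Section III (Study Objectives/Endpoints) of the combined protocol and SAP sets Specific aim #1 as the effect of the therapy on "time to (# of days) emergent and non-emergent healthcare utilization in patients with sleep-disordered breathing".

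The primary endpoint is "Composite end-point of time to occurrence of emergent healthcare utilization (such as re-hospitalization, unscheduled physician office visits, urgent care visits or emergency room visits". Office visits are qualified as unscheduled; re-hospitalization has no qualifier.

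Secondary endpoint 6 is "Composite end-point of time to occurrence of non-emergent healthcare utilization (such as scheduled hospitalization, scheduled physician office, urgent care visits or emergency room visits". Secondary endpoint 5 is "Time to re-hospitalization alone", again without a planned or unplanned qualifier.

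Events are collected by telephone. Under Day 60 in Section VI (Study Procedures), and in the same terms under Day 30, participants are asked whether they "had been admitted to this hospital, or had an unplanned visit to a" physician's office or emergency room. Section II (Study Design) describes the calls in similar terms. Sections II and VI also provide for collecting discharge summaries of re-hospitalizations and of office or ER visits, for the purpose of measuring costs.

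Section II sends deaths and hospitalizations to an adjudication committee of three site investigators but gives no criterion for emergent status. Section VII (Statistical Analysis) treats hospitalizations, office visits and ER visits as recurrent events and does not separate the two classes.

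**The concern.** Two endpoints meant to measure different kinds of care share named components. If an ER visit counts in both, a treatment effect confined to emergent care also moves the endpoint labelled non-emergent. A reader seeing both move together could take the second as independent support when the same visits produced both.

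The definition of the primary is affected too. A site recording an elective admission has no stated rule on whether it is a primary event. In an open-label trial, that leaves the decision to people who know the assigned arm.

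Data collection adds to the problem. The calls do not ask about the component that distinguishes endpoint 6, and they do not name one component of the primary.

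**Working it through.** **Reproducible figure.** The only sample-size figure in the plan (Section V) is enrolment: 60 / (1 − 0.25) = 80, which matches. The point does not depend on it. The documents give no rate for ER, urgent care or office visits. The 20.5% 30-day readmission figure does not split planned from unplanned admissions. The main check is therefore a comparison of the lists.

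**Components side by side**, with admissions split by whether they were planned:

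| Event | Emergent primary | Non-emergent endpoint 6 | Day 30/60 calls |
|---|---|---|---|
| Unplanned admission | listed | not listed | asked, no planned/unplanned split |
| Scheduled admission | not expressly excluded | listed | asked, no planned/unplanned split |
| Unscheduled office visit | listed | not listed | asked |
| Scheduled office visit | not listed | listed | not asked |
| Urgent care visit | listed | listed | not named |
| ER visit | listed | listed | asked, if unplanned |

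Of the four event types in endpoint 6, two are named in both lists, one (scheduled admission) may be shared depending on how the primary is read, and one (scheduled office visit) is unique to it. If the calls were the only source, every outpatient event reaching endpoint 6 would be an ER visit, which is also a primary event.

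**Possible readings of endpoint 6.**

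1. *Scheduled* qualifies only the hospitalization and office terms. ER and urgent care visits then count in both composites.
2. *Scheduled* qualifies the whole list. A scheduled ER visit is close to an empty category, and the primary's unqualified terms would still cover it.
3. The lists only illustrate *emergent* and *non-emergent*, and each visit falls on one side by its nature. The plan defines neither term, so the assignment cannot be made from it.

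**Illustrative size.** Assume constant, independent rates. Convert each 60-day probability p to a cumulative rate −ln(1 − p). The share of first endpoint 6 events that are ER or urgent care visits is then the ER/urgent care rate divided by the sum of the two rates. All probabilities here are assumptions.

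- ER or urgent care, p = 0.25: −ln(0.75) = 0.288
- Scheduled visit, p = 0.50: 0.693; share = 0.288 / (0.288 + 0.693) = 29%
- Scheduled visit, p = 0.70: 1.204; share = 0.288 / (0.288 + 1.204) = 19%
- Scheduled visit, p = 0.80: 1.609; share = 0.288 / (0.288 + 1.609) = 15%

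**Effect on the hazard ratio.** Let s be the share of endpoint 6's hazard that comes from shared components, and suppose the therapy does not affect scheduled care. The hazard ratio seen in endpoint 6 is (1 − s) × 1 + s × HR for emergent events. Both s and the hazard ratios below are assumed.

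| s | Emergent HR 0.70 | Emergent HR 0.50 |
|---|---|---|
| 10% | 0.97 | 0.95 |
| 25% | 0.925 | 0.875 |
| 50% | 0.85 | 0.75 |
| 75% | 0.775 | 0.625 |

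At small s the carry-over is slight; at large s endpoint 6 largely mirrors the primary.

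**The case against.** The strongest defence is the third reading above: both lists are introduced as examples, and the governing words are *emergent* and *non-emergent*. On that reading no visit need be counted twice. This stands against a claim that every ER or urgent care visit is double-counted. It does not remove the defect, because the plan gives no criterion for deciding which visits are which.

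A reader might also infer that elective admissions are primary events, since re-hospitalization is unqualified while office visits are not. The documents do not support that as fact. *Emergent* governs the primary's list, and endpoint 6 names scheduled hospitalization as non-emergent, which points the other way. What remains is an ambiguity.

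A reader might further infer that the trial cannot answer the non-emergent half of Aim 1. That goes too far: discharge summaries and visit records are to be collected, and reported events could be classified from them if the definitions were fixed first. The limit is that the plan describes no step for eliciting a scheduled or urgent care visit that the calls do not ask about.

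Finally, this is a pilot aiming for 60 completers, and the plan makes no confirmatory claim for endpoint 6. That is fair. It limits the consequences of double counting without justifying the overlapping definitions.

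**Conclusion.** The point holds as a defect of definition. Urgent care and ER visits are named in both composites, and no rule assigns an event to one. Followed as written, endpoint 6 partly repeats the primary instead of measuring non-emergent use. Whether an elective admission counts in the primary, and whether endpoint 5 means all or only unplanned re-hospitalization, is left open. The calls as described miss the component unique to endpoint 6 and do not name urgent care.

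This conclusion rests on the wording alone. The 15–29% range should not be read as an estimate for this trial. It uses assumed probabilities, holds the ER/urgent care probability at 25% throughout, and leaves out scheduled hospitalization. The amount of noise that elective admissions might add to the primary cannot be sized from the documents. The problem can be repaired before analysis, and the plan should be changed to do so.

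**What to change.** Fix mutually exclusive definitions before analysis:

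- **Primary:** unplanned re-hospitalization, unscheduled office visit, urgent care visit, ER visit.
- **Endpoint 6:** scheduled hospitalization and scheduled office visit only.
- **Endpoint 5:** state whether it covers all re-hospitalization or unplanned re-hospitalization only.

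Broaden the Day 30 and Day 60 questions to cover all admissions, all office visits (scheduled and unscheduled), urgent care visits and ER visits. Record planned or unplanned for each admission and office visit. Adding that label only to events already reported would not be enough, because it cannot recover visits that the calls never ask about. Confirm the classification against the discharge summaries and visit records already being collected.

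The cost is revised endpoint wording, a slightly longer call, and slightly fewer primary events if elective admissions would otherwise have been counted. No stated figure in the plan changes.
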